6.4 Risks and benefits

Close-range contacts between enumerators and household members present a particular risk for transmission of COVID-19 in communities with vulnerable populations. Precautionary measures to mitigate this risk are outlined in section 4.2.

For their time spent being interviewed, survey respondents will receive a monetary compensation. Pregnant women, recently delivered women, husbands of recently delivered women, nurse-midwives, ASBCs, and the heads of CSPS (who assist with the health facility observation checklist) will receive 1,000 CFA francs. Pregnant women who participate in the ANC observation and exit interview will receive 500 CFA francs.

6.5 Confidentiality

Precautions will be taken to ensure data confidentiality. Immediately after data collection, all data will be uploaded and stored securely in an IFPRI-server-based Dropbox Professional folder. To protect respondent confidentiality, only senior IFPRI researchers will have access to data and documents containing personally identifiable information. Research support staff and other project team members will have access to depersonalized data—located in a separate IFPRI-server-based Dropbox Professional folder—where direct identifiers have been replaced by randomly generated numeric IDs.

Data that is made publicly available will be carefully screened to remove any indirect and geographic identifiers which may breach the confidentiality of respondents.

6.6 Declaration of interests

The authors declare that they have no competing interests.

6.7 Access to data

All Co- and Principal Investigators of the project will have full access to the cleaned data. Other project team members will have access to data that has had all personally identifiable information removed.

In compliance with donor (Bill & Melinda Gates Foundation) open access policy requirements, fully anonymized datasets will be made publicly available one year after the end of the project. Metadata and other documentation of data collection procedures (such as the codebook, data collection instruments and interviewer guides/protocols) will also be made publicly available.

6.8 Ancillary and post-trial care

Not applicable.

6.9 Dissemination policy

Close engagement with the government of Burkina Faso is of high importance to the project. The A&T Burkina Faso team will be working in close partnership with government entities on strengthening maternal health systems at the national and regional levels throughout the duration of the project. Findings will be disseminated through in-country events, presentations, and conferences.

Within the research community, we aim to have the research peer-reviewed and published in high quality journals. Preliminary research findings may be presented at international conferences and internal IFPRI seminars.

VII. Timeline

7.1 Study timeline

Deliverables/Activities	2019												2020					
	Jan	Feb	Mar	Apr	May	Jun	Jul	Aug	Sep	Oct	Nov	Dec	Jan	Feb	Mar	Apr	May	Jun
1. Study protocol																		
Discuss study design with A&T	x	x	x	x														
Prepare study protocol					x	x												
2. Baseline data collection tools																		
Develop questionnaires/data collection tools						x	x											
Select and contract survey firm						x	x											
Translate questionnaire							x	x										
Program CAPI questionnaire								x	x									
8. Dietary assessment formative work																		
Review programming and conduct focus groups as needed									x									
Refine tools and questionnaires									x	x								
3. Local and US-based IRB approvals																		
IRB application at IFPRI							x											
IRB application in Burkina Faso							x											
4. Baseline survey implementation																		
Pretest, revise and finalize questionnaire									x	x								
Enumerator training										x								
Data collection											x	x						
5. Data cleaning and analyses																		
Data cleaning												x	x					
Data analyses													x	x	x	x	x	x
6. Baseline results																		
Prepare preliminary results														x	x			
Draft and finalize baseline results																x	x	
Prepare clean datasets																	x	

Deliverable/Activities	2020						2021						
	Jul	Aug	Sep	Oct	Nov	Dec	Jan	Feb	Mar	Apr	May	Jun	Jul
7. Study protocol													
Review study protocol				x									
8. Endline data collection tools													
Develop questionnaires/data collection tools				x	x								
Translate questionnaire					x								
Program CAPI questionnaire		x	x		x	x							
9. Local and US-based IRB approvals													
Obtain IRB approvals at IFPRI					x								
Obtain IRB approvals in Burkina Faso					x								
10. Endline survey implementation													
Pretest, revise and finalize questionnaire							x						
Enumerator training							x						
Data collection							x	x					
11. Data cleaning and analysis													
Data cleaning								x	x				
Data analyses									x	x	x	x	x
12. Endline results tables and datasets													
Draft endline results										x	x		
Finalize endline report and findings												x	x
Prepare clean datasets													x

References

## I. Study Background and Approach

In Burkina Faso, Alive & Thrive (A&T) has integrated a package of maternal nutrition interventions as part of the antenatal care (ANC) services provided by the government health system through system strengthening and social and behavior change communication (SBCC) approaches. Interventions are implemented in four health districts (two districts per region) in two regions – Boucle du Mouhoun (2 health districts) and Hauts Bassins (2 health districts). Key interventions include (1) maternal nutrition counseling (diet quality and quantity), (2) iron and folic acid (IFA) supplementation (adequate supply and counseling), (3) weight gain monitoring (measurement and interpretation), and (4) counseling on early initiation and exclusive breastfeeding practices. As per the 2016 WHO ANC guidelines (World Health Organization, 2016), A&T also promoted 8 ANC contacts during pregnancy, i.e., at least 4 visits at health facilities and 4 contacts in the community.

### 1.1 Research questions

The implementation research study addresses three research questions:

Research question 1 (RQ1)	What are the program impacts on maternal practices : (1) consumption of diversified foods and adequate intake of micronutrients, protein and energy compared to recommended intakes; (2) consumption of IFA supplements during pregnancy; and (3) early breastfeeding practices?
Research question 2 (RQ2)	Can the coverage and utilization of key maternal nutrition interventions (named above) and number of ANC contacts be improved through system strengthening and SBCC approaches?
Research question 3 (RQ3)	What factors influenced integration and strengthening of maternal nutrition interventions into the government ANC service delivery platform?

### 1.2 Impact evaluation study design

The impact evaluation of A&T's interventions used a cluster-randomized design with repeated cross-sectional surveys at baseline and endline. We applied stratified random allocation to 80 health centers (CSPS, Centre de Santé et de Promotion Social) within four health districts (Boromo, Toma, Dande, and Lena), which were assigned to either the A&T intervention (40 CSPS) or control areas (40 CSPS). The baseline survey was conducted in November-December 2019 and the endline survey was conducted in January-March 2021 in the same 80 CSPS catchment areas, thereby creating panel data at the CSPS level (not at individual level). Program implementation duration was approximately 12 months, with a couple of months of interruption due to the COVID-19 pandemic in March-April 2020.

### 1.3 Study sample

The two main study sample groups are: 1) pregnant women (PW), as this sample allows the assessment of dietary diversity and adequacy of micronutrient, protein and energy intake during pregnancy; and 2) recently delivered women (RDW) who have children less than 6 months of age, as this sample provides the best opportunity to assess the primary outcomes related to intervention exposure throughout pregnancy. PW and RDW were sampled separately but within the same CSPS catchment areas. For PW, we estimated a total sample size of 960 women (480 per arm) to detect a difference of 0.37 food groups in the mean dietary diversity score. For RDW, we estimated a total sample of 1920 women (960 per arm) to detect a difference of 15 tablets in the mean IFA tablets consumed after intervention.

Additionally, we included all husbands of RDW present at the time of the survey. Outside of the two main sample groups, nurses-midwives (N-M, 1 per CSPS) and community health workers (ASBC, within

1-3 villages per CSPS) were interviewed. Direct observations of ANC visits (2 per CSPS) to assess service quality, followed by exit interviews to assess service recall and client satisfaction, were conducted among pregnant women attending ANC at the time of the survey.

Table 1: Sample sizes

		Baseline 2019		Endline 2020	
Survey respondent type		Intervention	Control	Intervention	Control
Household survey:					
1	Pregnant women + 24h dietary recall	480	480	480	480
2	Recently delivered women with children <6 months	960	960	960	960
3	Husbands of RDW with children <6 months	960	960	960	960
Service provider survey:					
4	Nurses-midwives	40	40	40	40
5	Community health worker (ASBCs)	120	120	120	120
Observations:					
6	ANC observation + exit interview	80	80	80	80
Total:		2,640	2,640	2,640	2,640

## II. Outcome Measures and Indicators

Outcome measures corresponding to the three research questions are presented below. Only some outcome measures under RQ 1 pertain to the primary outcomes of the evaluation (i.e., used to test study hypotheses and arrive at a decision on overall study impact and to serve as basis to calculate the sample size); RQs 2 and 3 focus on secondary outcomes.

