2.4 Outcomes

The primary outcome indicators of the study are focused on diet quality and IFA supplementation. These include:

- 1) **Maternal dietary diversity among pregnant women**
 - i. Mean number of food groups consumed by pregnant women
- 2) **Use of iron-folic acid (IFA) supplements among RDW**
 - i. Mean number of IFA tablets consumed during pregnancy

The secondary outcomes relate to exposure to and utilization of key maternal nutrition, weight gain monitoring, and early breastfeeding interventions, as well as health worker knowledge and capacities at the points of service delivery. These include:

- 3) Maternal diet quality: proportion of pregnant women who achieve minimum dietary diversity; and micronutrient, protein and energy adequacy among pregnant women compared to the recommended dietary intake
- 4) Proportion of women who received 90+ IFA supplements during pregnancy
- 5) Early initiation of breastfeeding and exclusive breastfeeding practices of children
- 6) Use of ANC services (total number of ANC visits/contacts at facility and community levels and timing of the first ANC visit)
- 7) Exposure to nutrition interventions during ANC, including weight gain monitoring (proportion of women who are weighed and counselled about adequate weight gain, total number of times women are weighed during pregnancy)
- 8) Exposure to nutrition information from community health workers (proportion of women who were visited at home during pregnancy, total number of times visited), community groups, and other sources
- 9) Health worker knowledge on benefits and service provision for IFA supplementation, dietary diversity counselling, weight gain monitoring, and breastfeeding counselling
- 10) Availability of service supports (IFA supplies, records/registers, weight measurement equipment, counseling materials, and training and supervision for health workers)

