2.5 Sample size

The two main samples for the primary outcomes are: 1) pregnant women (PW) as this sample allows the assessment of diet quality during pregnancy; and 2) recently delivered women (RDW) who have children under 6 months of age, as this sample provides the best opportunity to assess the primary outcome related to intervention exposure throughout pregnancy (i.e., IFA consumption). Based on an initial mean dietary diversity score of 3.52 food groups across both regions and intra-cluster correlation of 0.110 from the 2019 baseline data (Kim et al., 2020), a significance level of 5% and power of 80%, the sample size of 480 PW per arm is estimated to detect a difference of 0.37 in the mean dietary diversity score after intervention.

For RDW, using an initial mean of 108.64 IFA tablets consumed across both regions and intra-cluster correction of 0.206 at baseline (Kim et al., 2020) and the same assumptions above for statistical significance, the sample size of 960 RDW per arm is estimated to detect a difference of 15 tablets in the mean IFA tablets consumed after intervention. If husbands of RDW are present at the time of the survey, they will also be interviewed briefly about their health and nutrition knowledge and any support provided during pregnancy. Approximately half of the expected sample size of husbands was available at baseline.

Outside of these two main samples, nurses-midwives (1 per CSPA) and community health workers (within 3 villages per CSPA) will be interviewed. In addition, direct observations of ANC visits (2 per CSPA) to assess service quality, followed by exit interviews to assess client satisfaction, will be conducted among a subgroup of pregnant women attending ANC at the time of survey.

The overall study samples sizes are presented in **Table 2**.

Table 2: Estimated sample sizes

	Baseline 2019		Endline 2020	
	Intervention	Control	Intervention	Control
Pregnant women	480	480	480	480
Women with children 0-5 months old	960	960	960	960
Husbands of women with children 0-5 months old	960	960	960	960
Nurses-midwives	40	40	40	40
Community health worker (ASBCs)	120	120	120	120
ANC observation & exit interview	80	80	80	80
Total	2,640	2,640	2,640	2,640

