### III. Statistical Analysis Plan

#### 3.1 General principles and methods

Data analyses will be performed using STATA version 16.0 (StataCorp LLC). All applicable statistical tests will be two-sided to allow potential findings of unexpected effects. Statistical significance will be presented at levels of  $p<0.05$ ,  $p<0.01$ , and  $p<0.001$ .

A diagram presenting the flow of clusters and individuals through the trial, based on the Consolidation Standard of Reporting Trials (CONSORT) statement: extension to cluster randomized trials (Campbell et al., 2012; Eldridge et al., 2016), is shown as follows.

[figure not shown]

Figure 1. CONSORT flow diagram for repeated cross-sectional surveys

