### 3.3 Impact estimates

The main analysis of impacts will be performed using intent-to-treat (ITT) specifications, wherein all study participants in the originally assigned program group at baseline are included in the statistical analysis and analyzed according to their program group, regardless of whether they received interventions or not. Women who refused or withdrew consent or those who are ineligible according to study protocol are excluded from ITT analysis.

The main impacts of the interventions will be estimated for: (1) maternal diet during pregnancy, (2) consumption of IFA supplements, and (3) early breastfeeding practices; secondarily, impact will be estimated for exposure to key interventions: (4) maternal nutrition counseling, (5) counseling on IFA supplementation, (6) weight gain monitoring and counseling, (7) breastfeeding counseling. The impact on dietary diversity will be assessed among PW, and impact on all the remaining outcomes will be assessed among RDW.

The difference-in-difference (DID) method will be used to estimate impacts by comparing the changes in outcomes over time (baseline vs. endline) between study arms (intervention vs. control). Point estimates and changes in the outcomes will be reported. For the analysis, the Stata *diff* command will be used, accounting for clustering at the CSPS level with a cluster version of Huber-White robust estimator of standard errors and using degrees of freedom appropriate for the number of CSPS (Hayes & Moulton, 2017). The fixed effects in the two-level regression models will be study arm, survey time, and arm times survey; the latter estimates the difference between arms in changes over surveys. We will conduct ITT analyses based on the original evaluation design, as well as the adjusted ITT analyses using the ITT groups but adjusting for gestational age (for PW only), maternal characteristics, child age and sex (for RDW only), and other variables that may be different between study arms.

Table 6: Dummy table for impact estimates

Indicator	Baseline		Endline		Unadjusted DID	Adjusted DID
	A&T (N=)	Control (N=)	A&T (N=)	Control (N=)		
	Mean (SD)	Mean (SD)	Mean (SD)	Mean (SD)	pp	pp
Dietary diversity score (number of food groups)						
Number of IFA tablets consumed						

	Percent	Percent	Percent	Percent	
Minimum dietary diversity ( $\geq 5$ food groups)					
Consumed 180+ IFA tablets					

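### Two primary outcomes feed one decision on overall impact with no rule to combine them: if either one suffices, the chance of a false claim is up to 9.75%, and if both are required, joint power is about 64%.

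*SAP*

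**What the plan says.** Protocol 2.4 states that "The primary outcome indicators of the study are focused on diet quality and IFA supplementation" and lists two: "Mean number of food groups consumed by pregnant women" and "Mean number of IFA tablets consumed during pregnancy". SAP Table 2 marks the same two as primary, the first from the PW survey and the second from the RDW survey. SAP section II gives the primary outcomes their role: they are "used to test study hypotheses and arrive at a decision on overall study impact".

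Protocol 2.5 sizes the PW sample with "a significance level of 5% and power of 80%, the sample size of 480 PW per arm", to detect 0.37 food groups. It carries the same assumptions over to 960 RDW per arm, to detect 15 tablets. The 5% is not divided between the two outcomes. SAP 3.1 makes tests two-sided and shows significance from p<0.05.

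None of the analysis sections (Protocol 4.4; SAP II, 3.1 and 3.3) says whether one or both outcomes must be significant, sets an order of testing, or adjusts for multiplicity.

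**The concern.** The SAP promises one decision and gives it two inputs, but leaves out the step that turns two p-values into that decision. The 5% and 80% in Protocol 2.5 describe each outcome alone. Whichever rule is applied later, at least one of these figures will not describe the overall decision.

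The gap matters most for a mixed result, with one outcome significant and the other not. The plan gives no answer there, so the rule could be chosen after the results are known. Protocol 1.1 says the findings are to inform scale-up by the health ministry and its partners, so the overall conclusion will be used.

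**Working it through.** **Inputs from the documents.** Two primary outcomes; 5% and 80% for each; 480 PW and 960 RDW per arm; differences of 0.37 food groups and 15 tablets; intra-cluster correlations of 0.110 and 0.206 (Protocol 2.5). There are 40 health centres per arm (SAP 1.2), so 480/40 = 12 PW and 960/40 = 24 RDW per cluster. PW and RDW are different women from the same catchment areas (SAP 1.3).

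**The plan's own figures.** The design effects are 1 + 11 × 0.110 = 2.21 for PW and 1 + 23 × 0.206 = 5.738 for RDW. No standard deviation is given, so the sample sizes cannot be reproduced independently. For a two-sided comparison of arms at endline they imply standard deviations of about 1.38 food groups and 49.0 tablets. The error-rate results below do not depend on these. The power results take the stated 80% at face value.

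**Rule A: either outcome suffices, no true effect on either.**
- Independent tests: 1 − (1 − 0.05)² = 0.0975, or 9.75%.
- The documents give no correlation between the two test statistics, so a range is assumed: 9.7% at 0.1, 9.5% at 0.3, 9.1% at 0.5.
- A rough ceiling on the correlation in one survey comes from shared clusters. The between-cluster share of the variance of a cluster mean is 12 × 0.110/2.21 = 0.597 for PW and 24 × 0.206/5.738 = 0.862 for RDW. With perfectly correlated cluster effects, the correlation is √(0.597 × 0.862) = 0.72, which gives 8.3%.
- False claims of benefit only, independent: 1 − 0.975² = 4.94%, against 2.5% for a single outcome.

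**Rule B: both outcomes must be significant.**
- Error with no effect on either, independent: 0.05² = 0.25%. It cannot exceed 5% under any dependence.
- Joint power, independent: 0.80 × 0.80 = 64%.

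**Rule C: either suffices, with Holm** (smaller p against 0.025, then the other against 0.05).
- Overall error is at most 5%.
- Power of one outcome at 0.025: Φ(1.9600 + 0.8416 − 2.2414) = Φ(0.5602) = 71.2%.
- Power per outcome, both effects real and independent: 0.712 + (0.800 − 0.712) × 0.712 = 77.5%.
- Power per outcome, only one effect real: 0.712 + (0.800 − 0.712) × 0.025 = 71.4%.
- Power for at least one success, both effects real and independent: 1 − (1 − 0.712)² = 91.7%, against 1 − 0.20² = 96% unadjusted.
- Detectable difference at 80% power for the first Holm test: factor (2.2414 + 0.8416)/(1.9600 + 0.8416) = 1.1005, giving 0.37 × 1.1005 = 0.41 food groups and 15 × 1.1005 = 16.5 tablets. This assumes two-sided sizing, which Protocol 2.5 does not state.

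**The case against.** The strongest reply is that these are two separate questions. The outcomes concern different practices, come from separately sampled and separately sized groups, and have their own rows in SAP Table 6. Two separate claims, each at 5%, need no adjustment. That would settle the matter if the SAP made two separate claims, but section II refers to one decision on overall impact. The reply therefore stands as a possible remedy, not as a description of the current text.

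Three stronger readings are tempting, and the documents do not support them.

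- *The false-claim rate is simply almost 10%.* With no rule stated, the rate is undetermined. The 9.75% requires that either outcome suffices, that neither has a true effect, that errors in both directions count, and that the tests are nearly independent.
- *Early breastfeeding is a third route to a claim.* SAP 3.3 does say that "The main impacts of the interventions will be estimated for: (1) maternal diet during pregnancy, (2) consumption of IFA supplements, and (3) early breastfeeding practices". But section II confines the decision to primary outcomes, and Table 2 lists every breastfeeding indicator as secondary. The wording in 3.3 separates effects on practices from exposure to the interventions; it does not create a third primary outcome.
- *Showing three significance levels adds error.* SAP 3.1 reads "Statistical significance will be presented at levels of" p<0.05, p<0.01 and p<0.001. This is a display convention. The loosest level is still 5%, and the stricter ones add no false positives.

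**Conclusion.** The gap is real, and its size depends on the missing rule. If either outcome suffices, the chance of a false overall claim is up to 9.75%, and about 8% to 9.75% over the assumed correlations. For benefit alone it is 4.94% against 2.5%, about double. If both must succeed, the error is controlled at 5%, but the 80% power becomes about 64% under independence.

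These figures count one test per outcome. SAP 3.3 plans both an unadjusted and an adjusted difference-in-difference estimate and names neither as decisive. Any freedom to choose between them comes on top and is not counted here.

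**What to change.** In SAP II and 3.1, state that overall impact is claimed if at least one of the two primary outcomes is significant by Holm: the smaller p-value against 0.025 and, if that passes, the other against 0.05. Name which difference-in-difference estimate supplies the p-values. The SAP describes the endline survey as completed, so record that the rule was fixed before the arms were compared.

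The cost is a few sentences and some power. Per outcome, power goes from 80% to about 77.5% when both effects are real, or about 71% when only one is. Put differently, the first test has 80% power for about 0.41 food groups or 16.5 tablets. No new data are needed.

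Two other choices would also close the gap, and the choice is the sponsor's:
- If both outcomes must succeed, keep 5% for each and restate joint power as about 64% under independence.
- If two separate claims are intended, delete the single decision on overall impact from section II and report each outcome on its own.
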